Randomized Trial of Hibiclens vs Benzoyl Peroxide Soap for Surgical Preparation

NCT04021524

Study Protocol and SAP

5/8/2020

Study Protocol

Adult male patients planning to undergo shoulder arthroplasty were assessed for eligibility by a research coordinator at their pre-operative appointment in the clinic. The study was confined to male patients because of their higher risk of Cutibacterium periprosthetic infections. Exclusion criteria were as follows: (1) self-reported skin sensitivity, (2) reported sensitivity or allergy to either chlorhexidine or benzoyl peroxide, (3) use of antibiotics within three months of surgical date, (4) use of medication for acne within three months of surgical date, and (5) lack of fluency in the English language. Patient age, sex, American Society of Anesthesiologist (ASA) classification, body mass index (BMI), and history of previous surgery on ipsilateral shoulder were recorded.

The patients were randomized by a research coordinator using simple randomization implemented through REDCap. The first group received a bottle of 4% chlorhexidine gluconate solution (CHG group). The second group received a bar of 10% benzoyl peroxide soap (BPO group). Both the chlorhexidine solution and benzoyl peroxide soap were stocked in the clinic so that all patients in each group received the same preparation. Both groups were instructed to apply the wash or soap to the surgical shoulder the night prior and the morning of surgery and to scrub for at least 60 seconds with the wash. The treating surgeon and all care providers were blinded to treatment group throughout the patient's care.

In the operating room, the unprepared, unshaved skin surface was sampled with a swab (Eswab™, #480C, Copan Diagnostics, Inc., Murrieta, CA) in the area of the planned incision. Four passes with the swab were taken by a surgical assistant wearing sterile gloves, turning the swab 90 degrees for each pass. The skin was then prepared with dual application of 2% CHG in 70% isopropyl alcohol and administration of intravenous antibiotics. Immediately after skin incision, swabs of the dermal wound edge were obtained in a similar fashion to the skin surface.

All specimens were processed by the laboratory in a Class 2 laminar flow biological safety cabinet. Specimens were inoculated onto the following microbiological media: blood agar (trypticase soy agar with 5% sheep blood), chocolate agar, Brucella agar (with blood, hemin, and vitamin K), and brainheart infusion broth. All media, with the exception of the Brucella agar, were incubated at 37 °C with 5% CO₂ for 21 days. Brucella agar plates were incubated anaerobically at 37 °C for 21 days. Plates were sealed in a manner that allows sterile aeration without desiccation. Media were examined daily for growth visually but were only opened if growth was noted.

The cultures results were reported in a semiquantitative manner as the Specimen Cutibacterium Value (SpCuV) across a range of 0 (no growth) to 4 (4+ positive growth on agar plates).

SAP

An a priori sample size calculation was performed using previous data regarding growth of Cutibacterium from the skin of shoulder arthroplasty patients. Based on pilot data combined with previous published data, we estimated the incidence of positive Cutibacterium cultures on the skin surface of male patients to be 77%. We determined the sample size of 50 was necessary to detect a reduction of 50% between the two groups with 1:1 allocation ratio, a power of 0.80, and an alpha of 0.05. Given that the intervention and outcome were only separated by 1 day, we anticipated a 0% dropout rate. Baseline demographics were compared between groups using a t test for continuous variables and a chi-square test for categorical variables. The two groups were compared with regards to the percent positivity of the skin surface and incised dermal edge as well as the bacterial load at each site using a chi-square test.

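### Does simple randomisation of 50 patients undermine the 1:1 ratio and the 0.80 power that the sample size assumes?

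*Combined protocol and SAP*

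**What the plan says.** On allocation, the Study Protocol says: "The patients were randomized by a research coordinator using simple randomization implemented through REDCap". It mentions no blocking or stratification. Patients "were assessed for eligibility by a research coordinator at their pre-operative appointment in the clinic", so the same role screens and randomises. One group receives a bottle of solution and the other a bar of soap.

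On size, the SAP states: "we estimated the incidence of positive Cutibacterium cultures on the skin surface of male patients to be 77" per cent, and then: "We determined the sample size of 50 was necessary to detect a reduction of 50% between the two groups". The design values behind that total are listed as follows: "with 1:1 allocation ratio, a power of 0.80, and an alpha of 0.05". Because intervention and outcome are a day apart, "we anticipated a 0% dropout rate". The comparison is by chi-square test. Nothing in the document fixes the final arm sizes at 25 each.

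**The concern.** The calculation uses equal arms, and its answer carries almost no margin: 25 per arm is the smallest whole number that reaches 0.80. Under simple randomisation an exact 25:25 split occurs in only 11.2% of trials, and about one trial in five ends at 20:30 or further apart. For a given total, unequal arms carry less information. It is natural to ask whether the stated power is really available, and whether permuted blocks would have secured it at no cost in patients. At stake would be an underpowered primary comparison and a wider confidence interval.

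**Working it through.** **Inputs.** From the SAP: control rate 0.77; 50% reduction, read as relative, so 0.385 in the other arm; power 0.80; alpha 0.05; total 50; no dropout. From the Study Protocol: simple randomisation. Assumed, because not stated: two-sided alpha, chi-square without continuity correction, assignment probability 0.5.

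**1. Reproduce the planned size.** With mean rate (0.77 + 0.385)/2 = 0.5775,

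n per arm = [1.960·√(2·0.5775·0.4225) + 0.8416·√(0.77·0.23 + 0.385·0.615)]² / 0.385²
= [1.960·0.6986 + 0.8416·0.6433]² / 0.1482 = 24.63.

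This rounds up to 25 per arm, 50 in total, as stated.

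**2. How far the arms can drift.** The size of one arm is Binomial(50, 0.5), which gives:
- exactly 25:25: 11.2%
- within 24:26: 32.8%
- 20:30 or worse: 2·P(X ≤ 20) = 20.3%
- 18:32 or worse: 6.5%
- 15:35 or worse: 0.7%

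**3. What a given split costs.** Formula power is Φ[(0.385 − 1.96·s₀)/s₁], where s₀ = √[p̄(1 − p̄)(1/n₁ + 1/n₂)], s₁ = √(0.77·0.23/n₁ + 0.385·0.615/n₂), p̄ is the weighted mean rate, and n₁ is the arm with the 77% rate.
- 25:25: (0.385 − 1.96·0.1397)/0.1287 = 0.864, power 0.806.
- n₁ = 20, n₂ = 30: (0.385 − 1.96·0.1439)/0.1294 = 0.796, power 0.787.
- n₁ = 30, n₂ = 20: (0.385 − 1.96·0.1404)/0.1332 = 0.824, power 0.795.

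| Split | Formula power | Exact power (uncorrected chi-square) | Effective N = 4n₁n₂/50 | 95% CI half-width, 1.96·s₁ (points) |
|---|---|---|---|---|
| 25:25 | 0.806 | 0.835 | 50.0 | 25.2 |
| 20:30 | 0.787–0.795 | 0.799–0.804 | 48.0 | 25.4–26.1 |
| 18:32 | 0.769–0.782 | 0.770–0.785 | 46.1 | 25.7–26.8 |
| Average over splits | 0.798 | 0.813 | 49.0 | – |

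The average effective N follows directly: E[n₁n₂] = 50·49/4 = 612.5, and 4·612.5/50 = 49.0. On average, simple randomisation costs one patient's worth of information and 0.806 − 0.798 = 0.8 points of formula power.

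**4. What blocks would give.** In simulated lists with random blocks of 4 and 6, the split is 25:25 in 77% of lists and 24:26 otherwise. Average power is 0.806 by formula and 0.836 exact.

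The exact gain of 2.3 points should not be taken at face value. At a common rate of 0.5775 the uncorrected test's true type I error is 6.2% at 25:25, against 5.5% averaged over simple-randomisation splits. Part of the extra power therefore comes from extra false positives. Fisher's test even reverses the comparison: 0.749 at 25:25 against 0.765 on average under simple randomisation. The formula's 0.8 points is the fairer measure.

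**5. What blocks would cost.** Someone who knows the past assignments and always guesses the arm that is behind is right for about 34.5 of 50 patients (69%) under random 4/6 blocks. Under simple randomisation the figure is 50%. Keeping the list hidden does not defeat that guess, which needs only the past assignments.

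**6. Scale.** If the true control rate were 75% rather than 77%, with the same relative reduction, formula power at 25:25 would be 0.779, a loss of 2.7 points. A two-point error in the planning rate thus costs over three times what simple randomisation costs on average.

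**The case for a change.** The strongest case for the concern is that the planned size has no slack, so small losses count. Formula power falls below 0.80 in about 40% of possible allocations under simple randomisation and in none under blocks of 4 and 6. The tail is real: in about one trial in 15 the split is 18:32 or worse, where formula power is at best 0.782 and can be 0.769 or lower. Blocks would remove that tail for the price of a new allocation list, or one or two extra patients would offset the average loss (average formula power 0.807 at 51 and 0.815 at 52).

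The arithmetic stands. The inference that the plan is deficient does not. Most of those 40% miss 0.80 by a fraction of a point to about one point: 22:28 gives 0.799 when the smaller arm has the 77% rate, and 20:30 gives 0.787 at worst. Exact power at 20:30 is about 0.80. A power target is a design-stage average under assumed rates, and that average is met within 0.2 points by formula and exceeded by the exact calculation. No stated figure is missed by enough to call for more patients.

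Nor are blocks free. The person who enrols also randomises, and bottle and bar cannot be confused, so past assignments are plausibly known to the recruiter. Simple randomisation then gives the strongest protection against anticipating the next assignment. The documents do not describe concealment beyond the use of REDCap, and that silence is no evidence that it was absent.

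**Conclusion.** The concern does not hold. Simple randomisation is a valid, unbiased method that meets a 1:1 target in expectation, and the planned chi-square test is valid at whatever arm sizes result. The SAP's 50 patients reproduce exactly, and the stated power of 0.80 is essentially delivered: 0.798 by formula and 0.813 by exact calculation, averaged over the splits that chance can produce. The average cost against perfect balance is 0.8 points of formula power, or one patient in 50. Blocking would recover that at the price of more predictable allocation, a trade-off on which competent statisticians can differ.

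This rests on a two-sided alpha of 0.05, a relative reading of the 50% reduction, equal assignment probability and an uncorrected chi-square test; the first two and the uncorrected formula together reproduce the stated 50. With a continuity correction, exact power would be about 0.75 even at 25:25. That shortfall would come from the choice of test and not from the method of randomisation.

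### Does a 0% dropout assumption that rests on a 1-day gap leave 50 patients too few, or leave open who is analysed?

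*Combined protocol and SAP*

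**What the plan says.** The sample-size part of the SAP takes a 77% positivity rate on the skin surface, a 50% reduction, 1:1 allocation, power 0.80 and alpha 0.05, and arrives at 50 patients. It then dismisses loss: "Given that the intervention and outcome were only separated by 1 day, we anticipated a 0% dropout rate".

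The Study Protocol gives the sequence of events. Patients "were assessed for eligibility by a research coordinator at their pre-operative appointment in the clinic". The third exclusion is "use of antibiotics within three months of surgical date" and the fourth is "use of medication for acne within three months of surgical date". Randomisation was done by a research coordinator "using simple randomization implemented through REDCap". On supply, "Both the chlorhexidine solution and benzoyl peroxide soap were stocked in the clinic". The product was used the evening before surgery and again that morning, and the swabs were taken in the operating room.

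The analysis sentence of the SAP reads: "The two groups were compared with regards to the percent positivity of the skin surface and incised dermal edge", and goes on to bacterial load, all by chi-square test. It names no analysis set.

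**The concern.** Two things look wrong.

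First, in a randomised comparison loss counts from allocation, not from first use of the product. The coordinator screens in clinic, the products are kept there, and the first wash precedes the day of surgery, so allocation at the clinic visit is a strong inference. The plan does not state it outright. A cancelled operation or a missed swab after that visit would lose the outcome, and the 1-day argument does not touch it. Because 50 carries almost no rounding margin, any loss would bring power under the stated 0.80 on the formula that yields 50.

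Second, exclusions 3 and 4 are anchored to surgery. A patient who starts an antibiotic or acne medication between the visit and the operation would come to meet them after allocation. If such patients were then dropped, the groups would be selected on a post-randomisation event and the comparability that randomisation gives would be weakened. No sentence on the analysis set expressly forbids this.

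**Working it through.** **Inputs.** From the SAP: p1 = 0.77, alpha 0.05, power 0.80, 1:1, N = 50. The 50% reduction is read as relative, so p2 = 0.385. Sidedness is not stated; two-sided is assumed. Loss rates are not in the documents, so every rate above zero below is an assumption.

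**Step 1: reproduce the 50.** Pooled two-proportion formula, no continuity correction, with mean proportion (0.77 + 0.385)/2 = 0.5775:

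n per arm = [1.960 × √(2 × 0.5775 × 0.4225) + 0.8416 × √(0.77 × 0.23 + 0.385 × 0.615)]² / 0.385²
= [1.960 × 0.6986 + 0.8416 × 0.6433]² / 0.1482
= 3.650 / 0.1482 = 24.63.

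Rounded up this is 25 per arm, 50 in total. The plan's figure is right on its own assumptions.

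**Step 2: power with equal arms.** Formula power is Φ[(0.385 × √n − 1.369)/0.6433]. At n = 25 this is Φ[(1.925 − 1.369)/0.6433] = Φ(0.864) = 0.806. The exact column enumerates every outcome of the uncorrected Pearson chi-square test.

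| Evaluable | Formula | Exact |
|---|---|---|
| 50 (25/25) | 0.806 | 0.835 |
| 48 (24/24) | 0.789 | 0.810 |
| 46 (23/23) | 0.771 | 0.782 |
| 44 (22/22) | 0.751 | 0.751 |

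Exact power does not fall smoothly: it is 0.792 at 24/25 but 0.810 at 24/24. With so few patients, the loss of one or two moves it around 0.80 rather than clearly below.

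**Step 3: simple randomisation and assumed loss.** Simple randomisation does not force 25/25. Let the number evaluable be Binomial(50, 1 − d) and the arm split Binomial(evaluable, 0.5), and average the power.

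| Loss d | Formula | Exact |
|---|---|---|
| 0 | 0.798 | 0.813 |
| 2% | 0.790 | 0.800 |
| 5% | 0.776 | 0.786 |
| 10% | 0.751 | 0.761 |

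The step from 0.806 to 0.798 at no loss (0.008) comes from unequal arms, not from dropout. Loss itself costs a further 0.02 or so at 5% (0.798 − 0.776) and about 0.05 at 10% (0.798 − 0.751). Averaged exact power is at least 0.80 until loss reaches about 2%, or 1 patient in 50.

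**Step 4: the analysis set, read against the protocol.** The Study Protocol fixes when eligibility is judged: at the clinic appointment. Exclusions 3 and 4 are listed as criteria for that assessment, so the surgical date in them is most naturally the planned date. No repeat check before surgery and no removal after allocation is described. The two groups are introduced immediately after the randomisation sentence, and the SAP compares the two groups. Following these sentences as written keeps patients in the arm to which they were randomised.

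**The case for a change.** The strongest case for a change is that the reason given for 0% is simply the wrong reason, whatever the true loss is, and that the analysis-set gap needs no assumed rate at all: two exclusion criteria are tied to a date after allocation, and no sentence protects against applying them then. The remedy would be a few sentences with no extra patients.

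Part of this stands. The 1-day argument does not address the time from clinic to surgery, and an explicit statement of when randomisation took place and who is analysed would be good practice.

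The rest does not carry a change. The moment of randomisation is inferred, the interval is not given, and a postponed operation need not lose the outcome, so 0% may be optimistic yet nearly right. Any sample size rounded up to its target without inflation has little reserve, so that alone is no fault. Quoting power at assumed losses would also place 0.798 at no loss beside the stated 0.80, a difference due to arm imbalance that has nothing to do with dropout. As for exclusions 3 and 4, the fact that no sentence forbids removal does not show that the plan calls for it.

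**Conclusion.** No change to the plan is needed. The 50 is correctly calculated, and the documents do not show that 0.80 is missed: at no loss, exact power of the uncorrected chi-square test is 0.835 with equal arms and 0.813 averaged over simple randomisation. At an assumed 5% loss the averaged exact figure is 0.786, which is 0.014 below target; at an assumed 10% it is 0.761. These rest on 77% versus 38.5%, a two-sided 0.05 test without continuity correction, and loss rates that the documents do not supply.

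The weak justification for 0% is a matter of wording. The unstated analysis set is a gap that an analyst would fill sensibly: each randomised patient with the relevant swab, in the assigned group, with eligibility settled at the clinic visit. The conclusion would differ only if the documents described a later eligibility check that removed randomised patients, or gave a material loss rate between visit and surgery. They do neither.

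### Do the planned significance tests on baseline demographics call for a change to the SAP?

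*Combined protocol and SAP*

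**What the plan says.** The Study Protocol section restricts enrolment to men ("The study was confined to male patients") and allocates patients "using simple randomization implemented through REDCap", with no blocking or stratification described. Five baseline items are collected: "Patient age, sex, American Society of Anesthesiologist (ASA) classification", "body mass index (BMI), and history of previous surgery on ipsilateral shoulder were recorded".

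The SAP section then says: "Baseline demographics were compared between groups using a t test for continuous variables and a chi-square test for categorical variables". It gives no purpose for these tests, no list of the variables tested and no rule for acting on a result. The next sentence sets out the outcome analysis: "The two groups were compared with regards to the percent positivity of the skin surface and incised dermal edge", together with bacterial load at each site, by chi-square test. No covariate or adjusted analysis appears anywhere in the document.

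**The concern.** A baseline test asks whether the arms differ by more than chance. Under correct randomisation that answer is already known. What a reader wants to know is whether an imbalance could distort the comparison of culture positivity. That depends on the size of the imbalance and on how strongly the variable predicts the outcome. The p-value reflects the first (with the sample size) and ignores the second.

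Two misreadings are possible. A non-significant row may be taken as proof of balance, and a significant row as proof of bias. With four variables that can be tested (sex is constant), and treating them as independent, at least one p < 0.05 would appear in 1 - 0.95^4 = 18.5% of correctly randomised trials. The SAP does not state that the outcome comparison is unadjusted by design, so one could worry that a significant row would prompt an unplanned adjusted analysis. Simple randomisation of only 50 patients makes visible chance imbalances fairly likely, which is why the point deserves a check.

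**Working it through.** **1. Does the planned outcome test match the plan's own sample size?** Inputs from the SAP: 77% positivity, a 50% reduction read as relative (77% to 38.5%), power 0.80, alpha 0.05 (two-sided assumed), 1:1 allocation.

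n per arm = [1.960 × √(2 × 0.5775 × 0.4225) + 0.842 × √(0.77 × 0.23 + 0.385 × 0.615)]² / 0.385²
= (1.369 + 0.541)² / 0.1482 = 24.6, rounded up to 25, or 50 in total.

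The stated 50 is reproduced, with power 0.806 at 25 per arm. The calculation is for an unadjusted comparison of two proportions, which is the test the SAP names. (Simple randomisation does not guarantee 25 per arm; equal arms are used below as the design case.)

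**2. What do the baseline tests detect at 25 per arm?**

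- t test: the smallest significant standardised difference is t(0.975, 48 df) × √(2/25) = 2.011 × 0.283 = 0.57.
- Chi-square without correction, 11/25 v 5/25: 50 × (11 × 20 - 5 × 14)² / (25 × 25 × 16 × 34) = 3.31, p = 0.069.
- 12/25 v 5/25: 50 × (12 × 20 - 5 × 13)² / (25 × 25 × 17 × 33) = 4.37, p = 0.037.

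One patient moves the result across 0.05, whatever the variable's relevance to the outcome. The general criticism is therefore right.

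**3. How often does a sizeable imbalance go unflagged?** Two binomial counts of 25 each, with the prevalence of a yes/no factor assumed because the documents give none:

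| Assumed prevalence | Imbalance of 5 or more patients | Share of these not flagged | Trials with an unflagged imbalance of 5 or more | Trials with an unflagged imbalance of 6 or more |
|---|---|---|---|---|
| 20% | 11.0% | 51% | 5.6% | 0.6% |
| 30% | 16.4% | 67% | 11.0% | 3.5% |
| 40% | 19.3% | 69% | 13.3% | 5.1% |

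The shares in the third column look large, but they apply to a minority of trials.

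**4. What would an unflagged imbalance do to the result?** Take the 11 v 5 split, 77% overall positivity and no treatment effect. The risk difference shifts by the covariate effect × (11 - 5)/25 = effect × 0.24. The false-positive rate is by exact enumeration.

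| Assumed covariate effect (points) | Shift in risk difference (points) | False-positive rate given this split |
|---|---|---|
| 0 | 0 | 5.5% |
| 10 | 2.4 | 5.8% |
| 20 | 4.8 | 6.8% |
| 30 | 7.2 | 8.4% |

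The design effect is 77 - 38.5 = 38.5 points. The test already stands at 5.5% with no covariate effect, so the excess due to imbalance is 0.3 to 2.9 points. The last row requires positivity of about 97% in one stratum (0.77 + 0.30 × 34/50 = 0.974). All these rates are conditional on an uncommon split. Averaged over randomisation, the simulated error of the unadjusted test stays near 5% (5.1-5.4% in step 5).

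**5. Would adjustment help?** Simulation of 20,000 trials per setting, N = 50, simple randomisation, 77% v 38.5% for power and 77% v 77% for type I error. Assumptions: 30% with previous surgery, standard-normal age, and the same odds ratio for previous surgery and per SD of age. The adjusted analysis is least squares on the 0/1 outcome.

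| Assumed odds ratio | Power, chi-square | Power, adjusted | Difference (points) |
|---|---|---|---|
| 1 | 0.821 | 0.794 | -2.8 |
| 1.5 | 0.811 | 0.803 | -0.8 |
| 2 | 0.810 | 0.828 | +1.7 |
| 3 | 0.817 | 0.876 | +5.9 |

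(Differences are from unrounded values.) Type I error was 5.0-5.2% adjusted and 5.1-5.4% for the chi-square.

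**6. Would acting on the baseline p-value help?** In a separate simulation (4,000 trials per setting, one covariate, adjusted only when its baseline test was significant), power was about 81-82%, the same as without adjustment. A test-then-adjust rule would add nothing, and the SAP does not contain one.

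**The case for a change.** The strongest case for a change is that it is cheap: two or three sentences would present the baseline table as means with SDs or counts with percentages, drop the p-values and commit to an unadjusted comparison. That would remove an invitation to misread the table and close the door on adjustment chosen after seeing it. A prespecified supportive model could also gain up to about 6 power points if the covariates are strongly prognostic.

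The statistical premise stands: these p-values do not measure whether an imbalance matters, and a descriptive table would read better. The rest carries less weight.

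- Because no decision hangs on the tests, removing them changes no result. Post hoc adjustment is conjecture about conduct; nothing in the SAP points to it.
- A single named chi-square with no covariates is already an unadjusted analysis. Saying so again would not alter what an analyst does.
- The recorded list includes sex in a trial of men only, so a chi-square on sex cannot be computed. But the SAP does not say sex is tested, and any analyst would leave out a constant.
- The gain from a supportive model depends entirely on assumed covariate strength. With unrelated covariates it costs nearly 3 points of power, and it would put a second estimate beside the main one in a 50-patient trial.

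**Conclusion.** No change to the plan is needed. Baseline p-values are uninformative about the harm an imbalance could do, but here they feed into nothing: the unadjusted chi-square is valid under simple randomisation, matches the sample size of 50, and is the only outcome test the SAP names. The sample size, the planned estimates and the conclusions are the same with or without the tests. Even the unfavourable 11 v 5 split adds only 0.3 to 2.9 points to the conditional false-positive rate under assumed covariate effects of 10 to 30 points, and unflagged imbalances of 6 or more occur in 0.6% to 5.1% of trials at assumed prevalences of 20% to 40%.

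The conclusion that nothing planned changes rests on the SAP's wording alone. The sizes rest on equal arms of 25 and on assumed prevalences, covariate effects and odds ratios, since the documents give none. Leaving the p-values out of the published table is a sensible presentational choice for the authors, and the plan does not have to be amended for it.

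### Does the SAP need to declare a primary outcome among its four chi-square comparisons?

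*Combined protocol and SAP*

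**What the plan says.** The sample-size text in the SAP concerns one quantity. It reads "we estimated the incidence of positive Cutibacterium cultures on the skin surface of male patients to be 77" per cent, and says that 50 patients were "necessary to detect a reduction of 50% between the two groups", with 1:1 allocation, "a power of 0.80, and an alpha of 0.05". The dropout sentence refers to a single outcome: "Given that the intervention and outcome were only separated by 1 day".

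The analysis sentence is wider. The arms are "compared with regards to the percent positivity of the skin surface and incised dermal edge as well as the bacterial load at each site". That makes four comparisons: positivity and load, each at the skin surface and at the dermal edge. The test is given only as chi-square, with no word on a continuity correction. Load is the SpCuV, which the Study Protocol describes as running "across a range of 0 (no growth) to 4 (4+ positive growth on agar plates)". Patients were allocated "using simple randomization implemented through REDCap", so the arms need not be exactly 25 and 25.

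The document nowhere calls an outcome primary or secondary. It gives no testing order and no division of alpha. It gives no assumed rate, effect or power for dermal-edge positivity or for load at either site.

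**The concern.** Four tests stand in one sentence, apparently as equals, and only one was sized. If skin-surface positivity proved not significant, nothing in the text would forbid presenting a dermal-edge or load p-value below 0.05 as the trial's finding. Read that way, the trial has four chances of a false positive instead of one, and three of them come from comparisons with no stated power.

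The unnamed test version adds to the doubt. At 50 patients a continuity correction changes both the error rate and the power appreciably. Leaving it open could also allow a choice after the p-values are known.

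**Working it through.** **Inputs from the SAP.** Control positivity 0.77, a 50% reduction, total N = 50, 1:1 allocation, power 0.80, alpha 0.05. **Assumed.** Two-sided testing, and the reduction read as relative, so 0.77 falls to 0.385.

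**1. Reproduce N.** With pooled variance and no correction, n per arm = [1.960·√(2·p̄·q̄) + 0.842·√(p₁q₁ + p₂q₂)]² / (p₁ − p₂)².

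- p̄ = (0.77 + 0.385)/2 = 0.5775, so √(2 × 0.5775 × 0.4225) = 0.6986.
- √(0.77 × 0.23 + 0.385 × 0.615) = √0.4139 = 0.6433.
- n = (1.369 + 0.541)² / 0.385² = 3.650/0.1482 = 24.6, hence 25 per arm and 50 in total.
- Power at 25 per arm = Φ[(0.385 × 5 − 1.369)/0.6433] = Φ(0.864) = 0.806.

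The stated N follows from skin-surface positivity with all of alpha spent on it. The main alternatives do not give 50: two-sided with continuity correction gives 60, and an absolute fall of 50 points (0.77 to 0.27) gives 30. One variant does also give 50, the one-sided corrected formula, so the match supports the two-sided uncorrected reading without proving it.

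**2. The sized test alone.** Exact binomial enumeration at N = 50. The averaged columns weight over the arm sizes that simple randomization produces; exactly 25/25 has probability 0.112.

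| Test version | Error (both 77%), 25/25 | Error, averaged | Power, 25/25 | Power, averaged |
|---|---|---|---|---|
| Pearson, uncorrected | 0.0545 | 0.0514 | 0.835 | 0.813 |
| N − 1 chi-square | 0.0545 | 0.0496 | 0.835 | 0.802 |
| Continuity-corrected | 0.0187 | 0.0206 | 0.749 | 0.720 |

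The uncorrected and N − 1 versions deliver the planned power at about 5% error. The corrected version does not reach 0.80 at N = 50; at N = 60 it has 0.811 (30/30) or 0.806 (averaged). None of these figures depends on the other three comparisons.

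**3. If any of the four could carry the claim.** Independent tests would give 1 − 0.95⁴ = 0.185. That overstates the risk, because positivity and load at a site come from the same culture.

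A null simulation (20,000 trials in each of 40 settings) allowed for this. Its assumptions, none of them given in the documents, were: dermal rate 10% to 60%, between-site correlation 0 to 0.9, flat or low-skewed load among positives, load analysed in five categories, and positivity taken as SpCuV above 0. The permutation version used 30 of these settings at 25/25, with 1,500 data sets each, and held every test at or below 5%.

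| Version | Any of four below 0.05 | Skin positivity not significant, another test is |
|---|---|---|
| Uncorrected 2×2 tests | 0.115–0.168 | 0.064–0.114 |
| Corrected 2×2 tests | 0.060–0.118 | 0.042–0.099 |
| Permutation tests | 0.075–0.122 | 0.053–0.099 |

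The permutation row is multiplicity alone; part of the excess in the uncorrected row is small-sample inflation.

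**4. Power at the dermal edge.** For a 50% reduction at 25/25, uncorrected, exact power is 0.081, 0.174, 0.257, 0.411 and 0.622 at assumed control rates of 10, 20, 30, 45 and 60%. Dermal-edge positivity could not have served as the sized outcome anywhere in this range.

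**The case for a change.** The strongest case for a change is that naming the primary outcome costs two sentences, leaves N at 50 and removes any argument about which result decides the trial. The two sites could well disagree: the skin swab is taken from unprepared skin, the dermal swab after skin preparation and intravenous antibiotics. A favourable dermal-edge result beside a null skin result is therefore a realistic outcome. Fixing the test version as well would stop anyone choosing it on the p-value.

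It is true that the label is absent and that the any-of-four error exceeds 5% in every setting examined. But that error belongs to a decision rule the documents never state, and its size rests wholly on assumed inputs. The sizing, the single alpha and the singular outcome all point to skin-surface positivity, which is also listed first in the analysis sentence.

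On the test version, writing the uncorrected Pearson test into the SAP would not be a clear gain. At 25/25 its exact error reaches about 6.5% when positivity is near 50%. The N − 1 version has a slightly lower averaged error (0.0496 against 0.0514) for slightly lower averaged power (0.802 against 0.813). Either is defensible, and the SAP's wording admits both.

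The benefit of a late declaration is also uncertain. The document is written in the past tense and does not show whether results by group were known. If they were, a label added now would help transparency but would not control error.

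**Conclusion.** The plan omits a label; it does not misstate a figure or rule. Skin-surface positivity is the only outcome with a rate, an effect and a power. N = 50 follows from it, and its test has 5.1% to 5.5% exact error and 0.81 to 0.84 exact power with the uncorrected chi-square at the planned rates. An analyst working from the sample-size paragraph would treat it as the main result, read the other three comparisons as supporting, and use a chi-square version consistent with the sizing.

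The 6% to 17% false-positive range is illustrative. It needs both a rule that the SAP does not contain and inputs that the documents do not give. The conclusion assumes two-sided testing, a relative 50% reduction and 50 as the total, all supported by the reproduction of N. It would weaken if a report rested its conclusion on a dermal-edge or load p-value alone, but that would be a fault of the report. No change to the plan is called for.
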